10.1.1.8 Visit 8/ Week 60 (Day 421 ± 7)

- Collect adverse events
- Record concomitant medication
- Data collection on IMP administration and IMP compliance check by review of diary and treatment kit.
- IVRS/IWRS contact for allocation of a batch number for treatment kit
- IMP kit dispensation and treatment administration package should be provided. The patient injection instruction manual and diary may be given, as needed.
- Reminders
 - An appointment will be given for the next visit.
 - Patient to bring the diary and used kits and unused auto-injectors at the next visit
 - Remind patient to be in fasting conditions (ie overnight, at least 10-12 hours fast and refrain from smoking) for next visit. Alcohol consumption within 48 hours and intense physical exercise within 24 hours preceding the next visit are discouraged.

10.1.1.9 Visit 9/ Week 72/ Month 18 (Day 505 ± 7)

- Collect adverse events
- Record concomitant medication
- Take vital signs including heart rate and blood pressure
- Get body weight measurement

- Physical examination
- Data collection on IMP administration and IMP compliance check by review of diary and treatment kit
- Obtain fasting blood sample for:
 - Lipids: measure or calculation of total-C, LDL-C, HDL-C, TG, non-HDL-C
 - Hematology
 - Chemistry
 - CPK
 - Liver panel
 - Anti-alirocumab antibodies
- Local urine pregnancy test (females of childbearing potential only).
- IVRS/IWRS contact for allocation of a batch number for treatment kit
- IMP kit dispensation and treatment administration package should be provided. The patient injection instruction manual and diary may be given, as needed.
- Reminders
 - An appointment will be given for the next visit.
 - Patient to bring the diary and used kits and unused auto-injectors at the next visit.

10.1.1.10 Visit 10/ Week 84 (Day 589 ± 7)

- Collect adverse events
- Record concomitant medication
- Data collection on IMP administration and IMP compliance check by review of diary and treatment kit.
- IVRS/IWRS contact for allocation of a batch number for treatment kit
- IMP kit dispensation and treatment administration package should be provided. The patient injection instruction manual and diary may be given, as needed.
- Reminders
 - An appointment will be given for the next visit.
 - Patient to bring the diary and used kits and unused auto-injectors at the next visit
 - Remind patient to be in fasting conditions (ie, overnight, at least 10-12 hours fast and refrain from smoking) for next visit. Alcohol consumption within 48 hours and intense physical exercise within 24 hours preceding the next visit are discouraged.

10.1.1.11 Visit 11/ Week 96 / Month 24 (Day 673 ± 7)

- Collect adverse events
- Record concomitant medication
- Take vital signs including heart rate and blood pressure
- Get body weight measurement
- Physical examination
- Review patient's diet. Patient should be on a NCEP-ATPIII TLC diet or equivalent.
- Data collection on IMP administration and IMP compliance check by review of diary and treatment kit
- Obtain fasting blood sample for:
 - Lipids: measure and/or calculation of total-C, LDL-C, HDL-C, TG, non-HDL-C, Apo B, Apo A-1, ratio Apo B/Apo A-1, and Lp (a)
 - Hematology
 - Chemistry
 - CPK
 - Liver panel
 - Anti-alirocumab antibodies
 - -
- Local urine pregnancy test (females of childbearing potential only).
- IVRS/IWRS contact for allocation of a batch number for treatment kit
- IMP kit dispensation and treatment administration package should be provided. The patient injection instruction manual and diary may be given, as needed.
- Reminders
 - An appointment will be given for the next visit.
 - Patient to bring the diary and used kits and unused auto-injectors at the next visit.

10.1.1.12 Visit 12/ Week 108 (Day 757 ± 7)

- Collect adverse events
- Record concomitant medication
- Data collection on IMP administration and IMP compliance check by review of diary and treatment kit.
- IVRS/IWRS contact for allocation of a batch number for treatment kit

- IMP kit dispensation and treatment administration package should be provided. The patient injection instruction manual and diary may be given, as needed.
- Reminders
 - An appointment will be given for the next visit.
 - Patient to bring the diary and used kits and unused auto-injectors at the next visit
 - Remind patient to be in fasting conditions (ie, overnight, at least 10-12 hours fast and refrain from smoking) for next visit. Alcohol consumption within 48 hours and intense physical exercise within 24 hours preceding the next visit are discouraged.

10.1.1.13 Visit 13/ Week 120/ Month 30 (Day 841 ± 7)

- Collect adverse events
- Record concomitant medication
- Take vital signs including heart rate and blood pressure
- Get body weight measurement
- Physical examination
- Data collection on IMP administration and IMP compliance check by review of diary and treatment kit
- Obtain fasting blood sample for:
 - Lipids: measure and/or calculation of total-C, LDL-C, HDL-C, TG, non-HDL-C
 - Hematology
 - Chemistry
 - CPK
 - Liver panel
 - Anti-alirocumab antibodies
- Local urine pregnancy test (females of childbearing potential only).
- IVRS/IWRS contact for allocation of a batch number for treatment kit
- IMP kit dispensation and treatment administration package should be provided. The patient injection instruction manual and diary may be given, as needed.
- Reminders
 - An appointment will be given for the next visit.
 - Patient to bring the diary and used kits and unused auto-injectors at the next visit.

10.1.1.14 Visit 14/ Week 132 (Day 925 ± 7)

Collect adverse events

- Record concomitant medication
- Data collection on IMP administration and IMP compliance check by review of diary and treatment kit.
- IVRS/IWRS contact for allocation of a batch number for treatment kit
- IMP kit dispensation and treatment administration package should be provided. The patient injection instruction manual and diary may be given, as needed.
- Reminders
 - An appointment will be given for the next visit.
 - Patient to bring the diary and used kits and unused auto-injectors at the next visit
 - Remind patient to be in fasting conditions (ie, overnight, at least 10-12 hours fast and refrain from smoking) for next visit. Alcohol consumption within 48 hours and intense physical exercise within 24 hours preceding the next visit are discouraged.

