Central Anti-alirocumab antibodies**	Х				Х		Х		Х		Х		Х		Х		Х	
	Х				Х						Х						Χ	
Quality of Life Variables																		
EQ-5D patient questionnaire	Χa			Χ	Х		Х										Χ	

- a. Investigations to be performed specifically for the entry in OLE at Day 1 (Visit 1) in addition to all investigations planned to be performed during the End of Double-Blind treatment visit of the parent study or for patients from the LTS11717, the visit V1 (Day 1) of the OLE study can occur at the time of the end of study visit, after the 8-week follow-up period.
- b. Pregnancy status should be checked by urine pregnancy testing on the Day 1 at visit 1 and during the OLE period.
- c. The end of treatment period visit of the Double-Blind parent study corresponds to the visit V1 (Day 1) of the OLE study, except for patient having participated in the LTS11717. These latter patients will have the opportunity to enter in the OLE study, after they have completed the parent study, including the 8-week follow-up period. For these patients, the visit V1 (Day 1) of the OLE study can occur at the time of the end of study visit, after the 8-week follow-up period.
- e. It is recommended a new diary to be dispensed to the patient at each visit starting from week 24, so that the compliance could be effectively checked at each visit
- * These visits are mainly dispensing visits
 ** Anti-alirocumab antibodies collections are to be done prior to the IMP injection, except for the EOT visit where no IMP injection is done.
- *** A follow-up safety call will be done 10 weeks after the last injection of alirocumab in case of premature discontinuation and for the patients who complete the study (see section 10.3.4).

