10.1.1.17 End-of-treatment visit: Visit 17/ Week 168/ Month 40 (Day 1177± 7)

The end of study is scheduled to be in second quarter 2017 or when the drug will become commercially available for the patient in the respective country whatever comes first. Thus, the End-of-treatment visit might be performed earlier than on Week 168 according to the date of inclusion of each patient in the OLE study, or if the patient early discontinues the study.

- Collect adverse events
- Record concomitant medication
- Take vital signs including heart rate and blood pressure
- Get body weight measurement
- Physical examination
- Review patient's diet. Patient should be on a NCEP-ATPIII TLC diet or equivalent.
- Data collection on IMP administration and IMP compliance check by review of diary and treatment kit
- IVRS/IWRS contact to document the end of treatment
- Obtain fasting blood sample for:
 - Lipids: measure and/or calculation of total-C, LDL-C, HDL-C, TG, non-HDL-C, Apo B, Apo A-1, ratio Apo B/Apo A-1, and Lp (a)

- Hematology
- Chemistry
- CPK
- Liver panel
- Anti-alirocumab antibodies

- Local urine pregnancy test (females of childbearing potential only).
- Completion of EQ-5D questionnaire by patient.
- Reminders
 - For all the patients, those who prematurely discontinue the treatment irrespective of the reason and those who will complete the study, an appointment will be given for the Follow up call. This phone call will have to be scheduled 10 weeks after last injection (+/- 7 days).

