10.1.2 Post-treatment Follow up period

End of Study Phone call: Visit 18/ Week 176 (\pm 7 days)

This phone call is to be done for all the patients, those who discontinue the treatment prematurely, whatever the reason, and those who will complete the study, and will take place approximately 10 weeks after the last injection of alirocumab.

- Collect adverse events
- Record concomitant medication, including any commercially available PCSK9 inhibitor different from alirocumab
- IVRS/IWRS contact to document the end of study

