#### General common rules

All safety analyses will be performed on the safety population as defined in Section 2.3.2, unless otherwise specified, using the following common rules:

- The parent baseline value is defined as the last available value obtained up to the date and time of the first double-blind IMP injection in the parent study.
- The OLE baseline is defined as the last available value obtained up to the date and time of the first OLE IMP injection.
- PCSA values are defined as abnormal values considered medically important by the Sponsor according to predefined criteria/thresholds based on literature review and defined by the Sponsor for clinical laboratory tests, vital signs, and ECG (PCSA version dated January 2009 [Appendix A]). Considering that the threshold defined in the PCSA list for monocytes and basophils can be below the ULN, the following PCSA criterion will be used for the PCSA analysis:
  - PCSA criterion for monocytes: >0.7 Giga/L or > ULN (if ULN ≥0.7 Giga/L)
  - PCSA criterion for basophils: >0.1 Giga/L or > ULN (if ULN ≥0.1 Giga/L)
- PCSA criteria will determine which patients had at least 1 PCSA during the TEAE period, taking into account all evaluations performed during the TEAE period, including nonscheduled or repeated evaluations.
- The treatment-emergent PCSA denominator for a given parameter will be based on the number of patients assessed for that given parameter at least once during the TEAE period.
- All measurements, scheduled or unscheduled, fasting or not fasting, will be assigned to analysis windows defined in Section 2.5.4, Table 1 in order to provide an assessment for all planned time points.
- For quantitative safety parameters based on central laboratory/reading measurements, descriptive statistics will be used to summarize results and change from baseline values by

visit using analysis windows. Summaries will also include the last on-treatment value and the worst on-treatment value. The last on-treatment value is defined as the last value collected during the treatment period (see Section 2.1.4). The worst on-treatment value is defined as the nadir and /or the peak value during the treatment period according to the direction (minimum or maximum) of the abnormality as defined in the PCSA list.

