# 2.4.5.3 Analyses of laboratory variables

The summary statistics (including number, mean, median, Q1, Q3, SD, minimum and maximum) of all laboratory variables (central laboratory values and changes from baseline) will be calculated for each visit or study assessment (baseline, each post-baseline value of the treatment period, last on-treatment and worst on-treatment value). In addition, for some parameters of interest, mean changes from baseline with the corresponding SE could be plotted over time (at same time points). This section will be organized by biological function as specified in Section 2.1.4.3. For glucose, only fasting samples will be summarized.

The incidence of PCSAs (list provided in Appendix A), as well as ALT increase as defined as AESI and hemoglobin decrease from baseline ≥15g/L, at any time during the TEAE period will be summarized by biological function irrespective of the baseline level and/or according to the following baseline status categories:

- Normal/missing
- Abnormal according to PCSA criterion or criteria

Glucose (quantitative summary and PCSA) will also be analyzed, overall and according to the diabetic status at baseline.

For parameters for which no PCSA criteria are defined, similar table(s) using the normal range could be provided.

Property of the Sanofi Group - strictly confidential

If any clinically significant signal is detected and need further characterization, exploration of time to onset will be performed for selected PCSAs assessed during the TEAE period as described below to account for the differential exposure time in all patients.

The incidence rates of selected PCSA during TEAE period at 24, 52, 78, 104 and 156 weeks of exposure will be calculated with Kaplan-Meier methodology, using the midpoint of the time interval between the first assessment with PCSA and the previous assessment. Kaplan-Meier curves will be also provided. Only the first event (PCSA) will be counted. Patients without any event will be censored at the last assessment performed during the TEAE period.

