#### 2.4.5.4 Analyses of vital sign variables

The summary statistics (including number, mean, median, Q1, Q3, SD, minimum and maximum) of all vital signs variables in sitting position (raw values and changes from baseline will be calculated for each visit or study assessment (baseline, each post-baseline value of the treatment period, last on-treatment, worst on-treatment value and follow-up visit). In addition for some parameters of interest; mean changes from baseline with the corresponding SE could be plotted over time (at same time points excepted follow-up visit).

Vital signs without position filled in will only be used for the PCSA analysis described below.

The incidence of PCSAs at any time during the TEAE period will be summarized.

If any clinically significant signal is detected and needs further characterization, exploration of time to onset will be performed for selected PCSAs assessed during the TEAE period as described below to account for the differential exposure time in all patients.

The incidence rates of selected PCSA during TEAE period at 24, 52, 78, 104 and 156 weeks of exposure will be calculated with Kaplan-Meier methodology, using the midpoint of the time interval between the first assessment with PCSA and the previous assessment. Kaplan-Meier curves will be also provided. Only the first event (PCSA) will be counted. Patients without any event will be censored at the last assessment performed during the TEAE period.

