# 2.5.4 Windows for time points

Data analyzed by time point (including efficacy, laboratory safety data, vital signs, quality of life, ADA) will be summarized using the analysis windows given in Table 1. These analysis windows will be applicable for all analyses, and they are defined to provide more homogeneous data for time point-specific analyses.

Table 1 - Analysis windows definition

Time point	Targeted study day	Analysis window in study days from OLE entry
Week 4	29	15 to 42
Week 8	57	43 to 70
Week 12	85	71 to minimum (98, study day corresponding to first the injection with IMP from kit allocated at Week 12 re-supply IVRS contact)
Week 24	169	155 to 182
Week 36	253	239 to 266
Week 48	337	316 to 357
Week 60	421	400 to 441
Week 72	505	484 to 525
Week 84	589	568 to 609
WeeK 96	673	652 to 693
Week 108	757	729 to 784
Week 120	841	813 to 868
Week 132	924	896 to 951
Week 144	1008	980 to 1035

Time point	Targeted study day	Analysis window in study days from OLE entry
Week 156	1092	1064 to 1119
Week 168	1176	1148 to 1203

Study days are calculated from the day of first OLE IMP injection, the day of first OLE IMP injection being Day 1. For enrolled but not treated patients, Day 1 is the day of visit 1.

.

If multiple valid values of a variable exist within an analysis window, the nearest from the targeted study day will be selected. If the difference is a tie, the value after the targeted study day will be used. If multiple valid values of a variable exist within a same day, then the first value of the day will be selected when time is available, else the scheduled visit will be selected.

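### SAP Table 1 departs from the protocol's assessment schedule: six dispensing-visit rows are open to by-visit safety summaries, and four target days are one day early (minor)

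*Protocol*

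**What the plan says.** **Protocol.** The flow chart (1.2) stars Visits 6, 8, 10, 12, 14 and 16, with the note "These visits are mainly dispensing visits". Sections 10.1.1.6, .8, .10, .12, .14 and .16 confirm what happens there: adverse events, concomitant medication, compliance and kit dispensing. No blood is drawn and no vital signs are taken. The follow-up contact in 10.1.2 is a call ("This phone call is to be done for all the patients") that collects adverse events and medication. Visit days follow a fixed pattern, including "Visit 14/ Week 132 (Day 925 ± 7" and, at end of treatment, "Visit 17/ Week 168/ Month 40 (Day 1177± 7".

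**SAP, time windows.** Table 1 in 2.5.4 has one row for each of Visits 2 to 17. It names laboratory safety data and vital signs among the data it governs and adds "These analysis windows will be applicable for all analyses". Day 1 is the day of the first OLE injection.

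**SAP, safety.** The common rules in 2.4.5 state: "All measurements, scheduled or unscheduled, fasting or not fasting, will be assigned to analysis windows defined in Section 2.5.4, Table 1". Statistics for laboratory variables "will be calculated for each visit or study assessment" (2.4.5.3). The vital-sign section (2.4.5.4) has parallel wording and extends the list to "last on-treatment, worst on-treatment value and follow-up visit".

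**SAP, lipids.** Sections 2.1.3 and 2.4.4.2 confine by-time-point results to the times at which the protocol plans lipid collection.

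**The concern.** Laboratory data and vital signs serve the primary objective, which is safety. Read literally, the safety text sends every value, planned or not, into Table 1 and reports it by visit, including in six weeks when nobody is due to be measured. A mean for Week 36 or Week 60 would then sit in the same table as means for Weeks 24, 48 and 72, although it describes a different and non-scheduled group of patients. The SAP states the needed limit for the secondary lipid endpoints but not for the primary safety data.

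The day numbering is a separate point. Table 1 should agree with the protocol and with the SAP's own definition of Day 1, and its last four rows do not.

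**Working it through.** **1. Target days.** With the first injection as Day 1, the target is 7 × week + 1. This gives the Table 1 target and the protocol day in all 12 rows from Week 4 to Week 120 (for example 7 × 120 + 1 = 841). The last four rows equal 7 × week instead:

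| Week | 7 × week + 1 | Protocol day | SAP target | SAP window | Protocol day ± 7 |
|---|---|---|---|---|---|
| 132 | 925 | 925 | 924 | 896–951 | 918–932 |
| 144 | 1009 | 1009 | 1008 | 980–1035 | 1002–1016 |
| 156 | 1093 | 1093 | 1092 | 1064–1119 | 1086–1100 |
| 168 | 1177 | 1177 | 1176 | 1148–1203 | 1170–1184 |

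The windows move with the targets. Around the protocol day they run −29/+26, against −28/+27 at Weeks 108 and 120. Every on-schedule visit still falls inside its window.

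The slip can also change which of two values in a window is nearest the target. A 56-day window holds 56 × 55 / 2 = 1,540 pairs of distinct days. Ties go to the later value, so the choice differs only when the two days sum to 2t + 1 or 2t + 2, where t is the SAP target. That is 27 + 26 = 53 pairs, or 3.4%.

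**2. Can a scheduled clinic visit reach a dispensing row?** Compare the latest permitted day of the preceding laboratory visit (protocol day + 7) with the first day of the row:

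| Row | Window | Length (days) | Preceding visit, latest day | Gap (days) |
|---|---|---|---|---|
| Week 36 | 239–266 | 28 | Week 24, Day 176 | 63 |
| Week 60 | 400–441 | 42 | Week 48, Day 344 | 56 |
| Week 84 | 568–609 | 42 | Week 72, Day 512 | 56 |
| Week 108 | 729–784 | 56 | Week 96, Day 680 | 49 |
| Week 132 | 896–951 | 56 | Week 120, Day 848 | 48 |
| Week 156 | 1064–1119 | 56 | Week 144, Day 1016 | 48 |

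The gap to the following clinic visit is larger in every row. No visit held within ± 7 days can land in these rows, which cover 280 days in total.

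**3. What can land there.** Three sources remain: unscheduled samples, clinic visits at least seven weeks off schedule, and end-of-treatment visits. The last group includes completers. Protocol 10.1.1.17 allows end of treatment before Week 168, depending on inclusion date or commercial availability, and 6.2.1 counts these patients as having completed. Their visit is 14 days after the last injection, inside the SAP treatment period (last dose + 21 days), so their values count.

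The enrolment span and launch dates are not given. As an assumption, spread completers' end-of-treatment days evenly over the last 12 to 78 weeks up to Day 1177. The share falling in a dispensing row is then:

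- 12 weeks: 27/85 = 32%
- 26 weeks: 56/183 = 31%
- 39 weeks: 104/274 = 38%
- 52 weeks: 112/365 = 31%
- 78 weeks: 168/547 = 31%

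**4. Where the SAP implies a limit.** Section 2.1.4.3 lists laboratory sampling at Weeks 0, 8, 24, 48, 72, 96, 120, 144 and 168 or early termination, with most liver tests also at Weeks 4 and 12. None of the six weeks is listed. Section 2.1.4.4 names the vital signs and gives no visits.

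**The case against.** Table 1 is a shared grid for several kinds of data, and a row does not oblige the sponsor to report every variable in it. With the sampling list in 2.1.4.3, the reference in 2.4.5 to planned time points most naturally means those planned for the variable concerned. That list also settles Weeks 4 and 12, where hematology, the wider chemistry panel and CPK are not drawn. Summaries show the number of patients, so a thin row would be visible. Plots over time are optional in the SAP. PCSA, last-value and worst-value analyses are unaffected.

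Most of this stands for laboratory data, where one sentence would turn an implied limit into a stated one. It does not cover vital signs, which have no visit list. Nor does it explain why the limit is explicit for lipids only.

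A reader might infer that these rows can contain only retests of abnormal results and patients leaving early, so that the tables would show false deterioration every 24 weeks. The documents do not support that. Completers' end-of-treatment samples can fall there too. A prompt recheck of a Week 24 result (latest on-schedule day 176) falls in the Week 24 window (to Day 182) or the unassigned gap to Day 238, not in the Week 36 window. By-visit quantitative laboratory summaries use central-laboratory values, so local retests do not enter.

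**Conclusion.** The point holds as a minor one.

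- **Six rows.** They have no scheduled laboratory or vital-sign assessment, and the safety text does not expressly exclude them. Any by-visit mean there describes a non-scheduled subset and is not comparable with the full-cohort visits. The documents give no rate of unscheduled sampling and no distribution of end-of-treatment dates, so neither the direction nor the size of the distortion can be derived. The 31–38% above rests on an assumed even spread and describes where completers' last visits might fall; it does not measure bias.
- **Follow-up vital signs.** The entry in 2.4.5.4 has no scheduled data behind it and would at worst produce an empty row.
- **Day numbering.** Four of 16 targets, with their windows, are one day early. Only values on a window boundary, or a choice between two values in one window, can change. The protocol headings are correct; the slip is in SAP Table 1.

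It would go too far to say that Table 1 ignores the visit schedule, since it lists every visit week from Visit 2 to Visit 17. It departs from the assessment schedule.

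**What to change.** 1. In SAP 2.4.5 and 2.5.4, state that by-time-point summaries and plots of each laboratory and vital-sign variable are limited to the time points at which protocol section 1.2 schedules that variable, and that other values are used only for PCSA and for last and worst on-treatment values. The six rows may stay in Table 1 for other uses, such as titration by visit (2.4.3.1).
2. Delete the follow-up visit from the vital-sign summaries in 2.4.5.4.
3. Correct the Table 1 targets to 925, 1009, 1093 and 1177, and the windows to 897–952, 981–1036, 1065–1120 and 1149–1204.

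The cost is a wording and table edit. Table 1 already leaves gaps between windows (for example Days 183–238), so keeping some off-schedule values out of by-visit tables is existing practice. Those values remain in the PCSA, last-value and worst-value analyses under their own definitions, so no safety information is lost.
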